6.4 GENERAL STATISTICAL ANALYSIS METHODS

Descriptive statistics for each variable will be calculated which will include measures of central tendency, variation, a frequency histogram and a count of the number of missing values.

When the arithmetic mean is found not to be an appropriate measure of central tendency, alternative statistics will be considered (e.g. median). When the distribution of a variable does not support the use of parametric statistics, nonparametric approaches or data transformations may be implemented. If data transformations are used they will be specified in the final clinical report.

6.4.1 ASSESSMENT OF COMPARABILITY OF RANDOMIZED GROUPS AND POOLABILITY OF INVESTIGATIONAL SITES

Summary tables describing the study population will be produced using subjects in the intent-to-treat population by randomized group. The study population will be described in terms of subject disposition, baseline characteristics, and concomitant medications. Subject disposition parameters will include number of subjects enrolled, treated, discontinued, and reasons for discontinuation. Baseline characteristics will include demographics, height, weight, BMI, and medical history.

The primary efficacy endpoint will be summarized by randomized group and investigational site in the observed intent-to-treat subjects. Although enrollment is set at a minimum of 20 subjects per site, if there is some unforeseen event preventing this minimum level of enrollment per site, investigational sites with fewer than 10 subjects will be combined for this purpose. A random center effect and a random center by randomized group (ITT) interaction will be included in the primary statistical model using logistic regression. If the p-value for the interaction term variance component is < 0.15 , the interaction term and the random center effect will be retained in the model and the effect of treatment will be estimated using this model as an additional analysis to the primary objective. If the p-value for the interaction term variance component ≥ 0.15 and the random center effect is < 0.05 , the random center effect alone will be retained in the model and the effect of treatment will be estimated using this model as an additional analysis to the primary objective. If neither is significant, the effect of treatment will not need to be re-estimated using a model that includes random center or center by treatment effects. The study is not powered to find a statistically significant treatment effect if significant center heterogeneity or effect modification is found, the models however, can be used to pool the data to assess the effect of center heterogeneity or effect modification on the estimated treatment effect.

6.4.2 HANDLING OF MISSING DATA

A sensitivity analysis to the missing data for the intent-to-treat primary efficacy endpoint analysis will be conducted. The sensitivity analysis will include a best-case, worst-case and tipping point analysis. The best-case analysis will impute successes for the subjects with missing data randomized to test group and failures for the subjects with missing data randomized to the control group. The worst-case analysis will impute failures for subjects with missing data randomized to test group and successes for subjects with missing data randomized to control group. The tipping point analysis completes the primary efficacy endpoint analysis with each possible combination of missing data imputation between the best- and worst-case analysis. The goal of the tipping point analysis is to determine at what level of imputation the statistical evaluation of the endpoint loses statistical significance. If the worst-case analysis maintains statistical significance, the tipping point analysis is not necessary.

6.4.3 EFFICACY ANALYSIS

6.4.3.1 PRIMARY EFFICACY ANALYSES

Subjects included in the analysis: All ITT subjects will be included in the analysis.

Endpoint: Subject response is defined as ≥ 20 mm² reduction in 2D submental area from baseline. The left and right side value at baseline will be averaged to result in the 2D submental area at baseline. The left and right side value at 90 days will be averaged to result in the 2D submental area at 90 days. In the event, only either the left or right side data is available, it will be used. Response will be calculated as baseline – 90 days. The evaluator that determines 2D submental area is blinded to follow-up and study group.

Hypothesis:

H₀: The proportion of responders at 90 days as compared to baseline for the test group is inferior as compared to the control group given a non-inferiority margin of δ , $p_{\text{control}} - p_{\text{test}} \geq \delta = 15\%$.

H_a: The proportion of responders at 90 days as compared to baseline for the test group is not inferior as compared to the control group given a non-inferiority margin of δ , $p_{\text{control}} - p_{\text{test}} < \delta = 15\%$

Sample Size Rationale: The sample size calculation assumes 73% response in both randomized groups. Power was set at 80%, one-sided Type I error controlled at 5%, a non-inferiority margin of 15% and PASS 12 Non-inferiority for two independent proportions using the Z-test with unpooled variance was used. The sample size requires 109 subjects per randomized group to have data necessary to calculate the primary endpoint. The total sample size of 218 was corrected for up to 16% attrition to arrive at 260 subjects randomized in the study.

Primary Statistical Analysis: The primary statistical analysis will be conducted using the observed data in the intent-to-treat patients using the Z-test (unpooled) for two independent proportions. Statistical significance is determined using a one-sided $\alpha=0.05$.

Additional Statistical Analysis: If there are intent to treat subjects with missing data, the analysis as specified in Section 6.4.1 Handling of Missing data will be conducted. The analysis in Section 6.4.1 regarding pooling will be conducted as specified in that section. The analysis will be completed for the subset of per protocol patients.

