4.5 SUBJECT RANDOMIZATION AND TREATMENT GROUP ASSIGNMENT

At the Treatment visit, only qualified study subjects (i.e., signed the IRB-approved consent form and confirmed eligible) will be randomly assigned according to a computer-generated 1:1 randomization to receive Ultherapy® treatment using either the Simulines or Standard transducers.

Randomizations will be stratified by site and will use randomly selected blocks of size 4 and 6 and will be generated by an electronic database in a reproducible fashion and will be provided to the site by electronic data capture the point that randomization occurs.

Enrolled subjects will be randomized to one of two treatment groups. Subjects and the study clinician performing efficacy assessments should remain blinded to the assigned treatment group. All randomized subjects will receive a single, dual depth lower face and neck Ultherapy® treatment. Group A will receive treatment with Standard transducers at EL2. The number of treatment lines in each region currently requiring an odd number of lines will be rounded up to an even number for equivalency between Standard and Simulines (e.g. if 15 lines are required in a region on the Standard transducer treatment map then this will be rounded up to 16 lines to match the 16 lines required on the Simulines map). Group B will receive treatment with Simulines transducers at EL2.

Subjects randomized to Group A will receive an Ultherapy® treatment to the lower face and neck with a total minimum pulse count of 672 pulses (+5%) at the 4.5mm and 3.0mm depths using Standard transducers. Energy levels for each transducer will be set to EL2:

- DS 4-4.5 at 0.9J with pitch of 1.5mm and 17 TCP's per line
- DS 7-3.0 at 0.30J with pitch of 1.1mm and 23 TCP's per line

Subjects randomized to Group B will receive a comparable treatment with a total minimum pulse count of 336 pulses (+5%) using the Simulines transducers at the 4.5mm and 3.0mm. Energy levels for each transducer will be set to EL2:

The assigned treatment group should be documented on the appropriate study-specific data form and study log.

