5.3.1 PRIMARY ENDPOINT

Efficacy will be assessed based on quantitative measurements of neck and submental lift at 90 days post-treatment compared to baseline. Subject response is defined as ≥ 20 mm² reduction in 2D submental area from baseline.

(Note: this is the same methodology and success criteria which supported the FDA clearance of the submental/neck lift indication for this device). Simulines transducers will be considered non-inferior to Standard transducers using a non-inferiority margin of 15% between the two study arms. The study was powered based on the expected response rate of 73% as seen in the pivotal trial supporting the neck/submental lift indication FDA clearance K121700. The observed response rate of the prior pivotal trial (73%) was higher than the minimum response rate required (65%) for success of the supporting trial.

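### Randomisation is stratified by site, but the primary Z-test ignores site and the site-adjusted logistic estimate has no stated route to the 15-point risk-difference margin

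*Combined protocol and SAP*

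**What the plan says.** - **Randomisation (Section 4.5).** "Randomizations will be stratified by site and will use randomly selected blocks of size 4 and 6".
- **Primary analysis (Section 6.4.3.1).** The comparison is made "using the observed data in the intent-to-treat patients using the Z-test (unpooled) for two independent proportions", at one-sided 0.05. The sample size uses the same test: "Non-inferiority for two independent proportions using the Z-test with unpooled variance was used".
- **Margin (Section 5.3.1).** "Simulines transducers will be considered non-inferior to Standard transducers using a non-inferiority margin of 15% between the two study arms". The hypotheses in Section 6.4.3.1 set it on the control rate minus the test rate, so it is a risk difference.
- **Site model (Section 6.4.1).** A random centre effect and a random centre-by-group interaction "will be included in the primary statistical model using logistic regression". If the interaction has p < 0.15, or failing that the centre effect has p < 0.05, "the effect of treatment will be estimated using this model as an additional analysis to the primary objective". The stated purpose is that the models "can be used to pool the data to assess the effect of center heterogeneity or effect modification on the estimated treatment effect". If neither is significant, nothing is re-estimated.
- **Small sites (Section 6.4.1).** For the summary of the primary endpoint by group and site, "investigational sites with fewer than 10 subjects will be combined for this purpose".

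**The concern.** There are three parts.

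1. **Design and analysis do not match.** Blocking within site removes most between-site variation from the difference between arms. The unstratified standard error still counts it, so the test is somewhat too cautious when sites have different response rates.
2. **The scale does not match.** A random-centre logistic model gives an odds ratio conditional on site. The margin is a difference in marginal response rates. The plan gives neither a conversion nor an odds-ratio margin. The model is used only when site differences have been flagged, which is when a reader will ask whether the 15-point conclusion survives. As written, the conversion would be chosen after seeing the data.
3. **The wording conflicts.** Section 6.4.1 attaches the word primary to the logistic model, while Section 6.4.3.1 gives that role to the Z-test. Section 6.4.3.1 settles which decides success, so this needs only tidying.

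At stake are a little power and an additional analysis that cannot be read against the margin. A false claim of non-inferiority is not the issue.

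**Working it through.** **Inputs from the plan.** 73% response in both arms; margin 0.15; one-sided 0.05; 80% power; 109 evaluable per arm; 16% attrition; 260 randomised (6.4.3.1). Up to 8 sites, 20 to 45 subjects each (2.2). 1:1 allocation in blocks of 4 and 6 within site (4.5).

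**Assumption.** The documents give no between-site SD of the response rate, so 0 to 0.20 is shown. Photography and head positioning are standardised across sites (4.6), which makes the low end plausible. At SD 0.10 the central 90% of site rates is 55% to 88%; at 0.17 it is 41% to 96%.

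**Step 1: reproduce the plan.**
- n per arm = (1.645 + 0.842)² × 2 × 0.73 × 0.27 / 0.15² = 108.3, so 109; total 218.
- 218 / 0.84 = 259.5, so 260.
- Power at 109 per arm = Φ(0.15 / √(2 × 0.73 × 0.27 / 109) − 1.645) = Φ(2.494 − 1.645) = 80.2%.

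**Step 2: what stratifying removes.** The response variance is 0.73 × 0.27 = 0.1971. With site SD s, the part s² lies between sites, and the stratified standard error is about √(1 − s²/0.1971) of the unstratified one.
- s = 0.10: ratio 0.974; stratified power ≈ Φ(2.494/0.974 − 1.645) = 82.0%.
- s = 0.17: ratio 0.924; stratified power ≈ Φ(2.494/0.924 − 1.645) = 85.4%.

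**Step 3: simulation.** 100,000 trials per setting: 260 randomised over 8 near-equal sites, blocks of 4 and 6, 16% random attrition, beta-distributed site rates. Size is at a constant 15-point deficit in every site. MH is the Mantel-Haenszel risk difference with Sato variance. Simulation error (95%) is about 0.25 points for power and 0.14 for size.

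| Site SD | Power, Z | Power, MH | Size, Z |
|---|---|---|---|
| 0 | 80.6% | 80.3% | 5.1% |
| 0.05 | 80.6% | 80.8% | 4.8% |
| 0.10 | 80.8% | 81.8% | 4.7% |
| 0.15 | 81.9% | 84.2% | 4.3% |
| 0.17 | 82.4% | 85.5% | 4.1% |
| 0.20 | 83.2% | 87.4% | 3.9% |

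MH size is 4.9% to 5.1% throughout. With uneven sites (20 to 45 subjects; 40,000 trials) the power gains are −0.1, 0.1, 1.0, 2.3, 2.8 and 3.9 points.

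**Step 4: the price of stratifying.** If the odds ratio is constant, the risk difference varies between sites. For a wider population of sites, MH size is then 4.9% at SD 0.05, 5.3% at 0.10, 5.9% at 0.17 and 6.9% at 0.20, against 4.6% to 4.9% for the Z-test. For the sites actually in the trial, MH size stays at 5.0% to 5.1%. The variance must be named: the Greenland-Robins form gives 5.4% to 5.7% even with no site differences.

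**Step 5: the scale gap.** A 15-point deficit, as an odds ratio:
- control 65%: (0.50/0.50) / (0.65/0.35) = 0.54
- control 73%: (0.58/0.42) / (0.73/0.27) = 0.51
- control 85%: (0.70/0.30) / (0.85/0.15) = 0.41

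Conversely, the odds ratio of 0.51 is a deficit of 16.3 points at 65%, 15.0 at 73% and 10.7 at 85%. One odds ratio can lie on either side of the margin, depending on the control rate.

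**The case against.** The strongest reply is that nothing in the primary analysis is wrong. The Z-test is valid, matches the sample-size method, keeps its power and does not inflate size when the deficit is the same at every site. The gain from stratifying is close to nil where site differences are plausible. All of that stands.

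It can also be said that in a non-inferiority trial the error to guard against is a false claim, and that for a wider population of sites the stratified test can exceed 5% while the Z-test does not. That also stands, although the excess is about 0.3 points at SD 0.10 and disappears for the trial's own sites. Limiting inference to those sites is a real narrowing, since Section 6.4.1 treats centre as random. It has to be stated openly.

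Finally, Section 6.4.1 already summarises the primary endpoint by group and site, and its logistic model is conditional, additional and decides nothing. True, but a table of site rates is not an adjusted estimate with a confidence limit. The model's stated purpose, to show what site heterogeneity does to the treatment effect, needs the scale on which the primary result is judged.

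**Conclusion.** The concern holds in all three parts, and its size is modest. The primary conclusion is not at risk: if the site SD lies between 0 and 0.20 and the deficit is the same at every site, the Z-test's size is 3.9% to 5.1% and its power is at or above plan. Stratifying by site would recover about 1 point of power at SD 0.10, and 3 to 4 points only in extreme cases. The scale gap matters more. If the site model is triggered, its result has no prespecified reading against the 15-point margin. These figures rest on the assumed site SD, random attrition and 8 sites. The change is worth making because it is cheap and leaves the sample size and the margin as they are.

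**What to change.** Before unblinding:

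1. **Section 6.4.3.1.** Make the primary analysis the Mantel-Haenszel risk difference stratified by site, with the Sato variance, in ITT subjects with observed data. Combine sites with fewer than 10 subjects, as 6.4.1 does for its by-site summary. Conclude non-inferiority if the upper one-sided 95% limit for control minus test is below 15 points. Keep the unstratified unpooled Z-test as a sensitivity analysis. State that inference is for the participating sites, and that size for a wider population of sites can modestly exceed 5% if the risk difference varies between sites.
2. **Section 6.4.1.** Report the site-adjusted effect as a risk difference with its confidence limit, for example by standardising the logistic model over the trial's sites. Reword the reference to the primary statistical model to agree with 6.4.3.1.

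**Cost.** A few lines of text and code. Because Section 6 is part of the protocol, Section 14 requires the change to go through as an amendment. No data or subjects are added: with no site differences, stratified power is 80.3% against 80.6%, so 109 evaluable per arm and 260 randomised still suffice. The statistical price, for a wider population of sites only, is an excess in size of about 0.3 points at SD 0.10 and 0.9 at 0.17.

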6.4.3.2 SECONDARY EFFICACY ANALYSES

The secondary efficacy analyses will be performed using subjects in the intent to treat population who have a non-missing assessment for the efficacy parameter at the time point being analyzed. The secondary endpoints are supportive in nature and are evaluated to provide additional information and are not intended to support additional claims. Descriptive statistics may be included in the labelling and for this purpose are defined as number of observations, mean, standard deviation, median, minimum and maximum for continuous variables and number and proportion of observations for categorical variables. The secondary outcomes may additionally be completed for the subset of per protocol patients.

Secondary efficacy outcomes will be:

6.4.3.2.1 Quantitative improvement measurements of submandibular and submental lift at 180 and 365 days post-treatment compared to baseline.

Endpoint: Subject response is defined as $\geq 20 \text{ mm}^2$ reduction in 2D submental area from baseline. The left and right side value at baseline will be averaged to result in the 2D submental area at baseline. The left and right side value at 180 days will be averaged to result in the 2D submental area at 180 days. Similarly, at 365 days. In the event, only either the left or right side data is available, it will be used. Response will be calculated as baseline – follow-up. The evaluator that determines 2D submental area is blinded to follow-up and study group.

Statistical Analysis: A repeated measures model will be used to analyze the data from this objective. The dependent variable will be response (y/n). The independent variables will be study group and day of follow-up. A covariance structure will be used to account for the correlation expected among the repeated observations collected for each subject. The covariance structure that fits the data best, i.e. results in the lowest Schwarz Bayesian Information Criteria (BIC) value all else held constant will be used, among the

unstructured, compound symmetric or auto-regressive types. Statistical significance will be determined using a two-sided $\alpha=0.05$.

6.4.3.2.2 Comparison of improvement in overall lifting and tightening of skin as determined by a masked, qualitative assessment of photographs at 90, 180 and 365 days post-treatment compared to baseline.

Endpoint: The proportion of “Improved, correct pre-post selection” out of the total number of responses. The total number of responses includes the number responding “Improved, correct pre-post selection”, “Improved, incorrect pre-post selection” and “No change”.

Statistical Analysis: A repeated measures model will be used to analyze the data from this objective. The dependent variable will be the proportion meeting the endpoint. The independent variables will be study group and day of follow-up. A covariance structure will be used to account for the correlation expected among the repeated observations collected for each subject. The covariance structure that fits the data best, i.e. results in the lowest Schwarz Bayesian Information Criteria (BIC) value all else held constant will be used, among the unstructured, compound symmetric or auto-regressive types. Statistical significance will be determined using a two-sided $\alpha=0.05$.

6.4.3.2.3 Assessment of mean change and ≥ 1 point improvement from baseline to 90 days post treatment on the validated, Merz Jawline Grading Scale (MJGS) by an independent masked evaluator.

Endpoints: Change in MJGS from baseline to 90 days and proportion of subjects with a ≥ 1 point improvement from baseline to 90 days post treatment. Three masked evaluators that will review subject photos and will be blinded to treatment assignment and follow-up.

Statistical analysis: The mean change in MJGS from baseline to 90 days will be compared between study groups using the Two-sample T-test. The proportion of subjects with ≥ 1 point improvement from baseline to 90 days post treatment will be compared using Fisher’s exact test.

6.4.3.2.4 Quantificare 3D imaging of up to 135 study subjects to assess volumetric changes from baseline compared to 90, 180, and 365 days post-treatment.

Endpoints: Change in volume as calculated per the Quantificare 3D imaging system (see Appendix I) from baseline to 90, 180 and 365 days post-treatment. The evaluator that determines Quantificare volume is blinded to follow-up and study group.

Statistical Analysis: A repeated measures model will be used to analyze the data from this objective. The dependent variable will be change in volume. The independent variables will be study group and day of follow-up. A covariance structure will be used to account for the correlation expected among the repeated observations collected for each subject. The covariance structure that fits the data best, i.e. results in the lowest Schwarz Bayesian Information Criteria (BIC) value all else held constant will be used, among the unstructured, compound symmetric or auto-regressive types. Statistical significance will be determined using a two-sided $\alpha=0.05$.

6.4.3.2.5 Patient satisfaction and patient reported improvement at 90 days post-treatment.

Endpoints: Patient reported satisfaction and patient reported improvement (see Appendix E) at 90 days post-treatment.

Statistical Analysis: The number and percent of respondents to each of the questions and categories will be summarized by study group.

6.4.3.2.6 Comparison of average treatment times using Simulines transducers compared to average treatment times using Standard transducers.

Endpoint: Treatment time as defined as the time treatment started and the time the treatment concluded as captured per the treatment log.

Statistical Analysis: Treatment time will be compared by study group using the Two-sample T-test.

6.4.3.2.7 Comparison of average pain scores using a validated Numeric Rating Scale to assess subjects' treatment-related comfort level with Simulines transducers versus Standard transducers.

Endpoint: Pain as measured using the validated numeric rating scale (Attachment D).

Statistical Analysis: A repeated measures model will be used to analyze the data from this objective. The dependent variable will be pain score. The independent variables will be study group, transducer depth (4.5 mm, 3.0 mm) and treatment location (cheeks, submandibular/submental). A covariance structure will be used to account for the correlation expected among the repeated observations collected for each subject. The covariance structure that fits the data best, i.e. results in the lowest Schwarz Bayesian Information Criteria (BIC) value all else held constant will be used, among the unstructured, compound symmetric or auto-regressive types. Statistical significance will be determined using a two-sided $\alpha=0.05$.

6.4.3.2.8 Subject Global Aesthetic Improvement Scale (SGAIS) results assessing overall aesthetic improvement at 90, 180 and 365 days post-treatment.

Endpoint: SGAIS as measured at 90, 180 and 365 days post treatment.

Statistical Analysis: The number and percent observed in each category will be reported by randomized group for each follow-up. A repeated measures model will also be used to analyze the data from this objective. The dependent variable will be improved (y/n) with independent variables study follow-up and study group. A covariance structure will be used to account for the correlation expected among the repeated observations collected for each subject. The covariance structure that fits the data best, i.e. results in the lowest Schwarz Bayesian Information Criteria (BIC) value all else held constant will be used, among the unstructured, compound symmetric or auto-regressive types. Statistical significance will be determined using a two-sided $\alpha=0.05$.

6.4.3.2.9 Clinician Global Aesthetic Improvement Scale (CGAIS) results assessing overall aesthetic improvement at 90, 180, and 365 days post-treatment.

Endpoint: CGAIS as measured at 90, 180 and 365 days post treatment.

Statistical Analysis: The number and percent observed in each category will be reported by randomized group for each follow-up. A repeated measures model will also be used to analyze the data from this objective. The dependent variable will be improved (y/n) with independent variables study follow-up and study group. A covariance structure will be used to account for the correlation expected among the repeated observations collected for each subject. The covariance structure that fits the data best, i.e. results in the lowest Schwarz Bayesian Information Criteria (BIC) value all else held constant will be used, among the unstructured, compound symmetric or auto-regressive types. Statistical significance will be determined using a two-sided $\alpha=0.05$.

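### The Day 180/365 response model omits the Day-90 response measured the same way, so its proportions may be biased, in either direction, if dropout after Day 90 depends on that response

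*Combined protocol and SAP*

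**What the plan says.** Section 6.4.3.2.1 covers "Quantitative improvement measurements of submandibular and submental lift at 180 and 365 days post-treatment compared to baseline". A subject responds if the 2D submental area, averaged over the two sides, has fallen by at least 20 mm² from baseline. Response (yes/no) enters a repeated measures model with study group and follow-up day as the only independent variables. The covariance structure is the one with the lowest BIC among unstructured, compound symmetric and autoregressive. Under 6.4.3.2, each secondary analysis takes the ITT subjects "who have a non-missing assessment for the efficacy parameter at the time point being analyzed".

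Section 6.4.3.1 uses the same threshold, side-averaging and blinded evaluation at Day 90. The other multi-visit outcome models (masked photographs, 3D volume, SGAIS, CGAIS) all include Day 90; 6.4.3.2.8, for instance, takes "SGAIS as measured at 90, 180 and 365 days post treatment". The best-case, worst-case and tipping-point analyses in 6.4.2 are confined to the primary endpoint.

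Section 6.4.3.2 describes the secondary endpoints as supportive and disclaims additional claims. It then adds "Descriptive statistics may be included in the labelling", which for a response endpoint means the number and proportion observed.

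**The concern.** As written, the analysis estimates response among subjects measured at the later visits. Someone measured at Day 90 and at neither Day 180 nor Day 365 drops out of the model, although an earlier result on the same measure is in the database. If Day-90 response predicts later response and is also related to who leaves, those who return are not representative of the randomized subjects, and the planned model has nothing with which to correct this. No missing-data sensitivity analysis covers these visits.

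At stake is the accuracy of the trial's quantitative evidence on durability, which may appear in labelling as observed proportions. The omission also looks unintended. The other longitudinal outcome models use three visits, and with only two visits compound symmetry and first-order autoregression are the same structure (one variance, one correlation), so BIC cannot choose between them.

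**Working it through.** **The plan's own sizing.** Section 6.4.3.1 states: "The sample size calculation assumes 73% response in both randomized groups". With a 15-point margin, one-sided alpha 0.05, 80% power and the unpooled Z-test:

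n per arm = (1.645 + 0.842)² × 2 × 0.73 × 0.27 / 0.15² = 108.3, rounded up to 109 (power 80.2%). Total 218; 218 / (1 − 0.16) = 259.5, rounded up to 260. The plan's figures reproduce. The 16% is an upper allowance for loss of Day-90 data. No figure is given for loss after Day 90.

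**Bias in the later proportion.** Let p be Day-90 response, a and b the later response rates in Day-90 responders and non-responders, d the overall loss after Day 90, and k the ratio of non-responder to responder dropout.

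- Responder dropout d1 = d / [p + (1 − p)k]; non-responder dropout d0 = k × d1.
- Full-cohort later response = p·a + (1 − p)·b.
- Responder share among returners q = p(1 − d1) / (1 − d).
- Bias = (a − b)(q − p).

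Only p = 0.73 comes from the plan; a, b, d and k are assumptions. Take a = 0.85 and b = 0.20, so the full-cohort rate is 0.73 × 0.85 + 0.27 × 0.20 = 67.4%. For d = 0.16 and k = 2: d1 = 0.16/1.27 = 0.126; q = 0.73 × 0.874/0.84 = 0.7596; bias = 0.65 × 0.0296 = +1.9 points. Over the range, in percentage points:

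| Loss after Day 90 | k = 0.5 | k = 1 | k = 2 | k = 3 |
|---|---|---|---|---|
| 5% | −0.4 | 0 | +0.5 | +0.9 |
| 10% | −0.8 | 0 | +1.1 | +1.8 |
| 16% | −1.4 | 0 | +1.9 | +3.2 |
| 25% | −2.5 | 0 | +3.4 | +5.5 |

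With weaker persistence (a = 0.80, b = 0.30) and 16% lost, the bias is +1.5 points at k = 2 and +2.4 at k = 3. If a = b it is zero whatever the dropout. If all of a 16% loss were Day-90 non-responders, it would be +9.0 points (+7.0 with weaker persistence).

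**Does adding Day 90 help?** A random-intercept logistic model was fitted by maximum likelihood to 40,000 simulated subjects with 16% lost after Day 90. Full-data response was 67.6% at Day 180 and 61.8% at Day 365. The within-subject correlation was assumed.

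| Dropout ratio k | Days 180 and 365 only | With Day 90 added |
|---|---|---|
| 0.5 | 66.6% / 60.8% | 67.6% / 61.8% |
| 1 | 67.6% / 61.9% | 67.6% / 61.9% |
| 2 | 69.1% / 63.5% | 67.6% / 62.0% |
| 3 | 70.0% / 64.4% | 67.6% / 61.9% |

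The correction works in both directions and does no harm when dropout is unrelated to response.

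**Arm contrast.** Suppose Day-90 response is 73% and 63% in the two arms, a = 0.8, b = 0.2, and dropout is 10% in responders and 32% in non-responders.

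- Full cohort: 63.8% and 57.8%, difference 6.0 points.
- Returners: q = 0.657/0.8406 = 0.782 and 0.567/0.8186 = 0.693, giving 66.9% and 61.6%, difference 5.3 points.

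The 0.7-point change compares with a standard error of √(2 × 0.64 × 0.36/109) = 6.5 points. The slope of q in p is 0.90 × 0.68 / [0.68 + 0.22p]². It falls below 1, and the contrast shrinks, only when p exceeds about 46%; below that the contrast widens.

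**The case against.** A reader might infer that durability is overstated and that non-responders disappear. The documents do not support that. Upward bias needs Day-90 non-responders to leave more often and Day-90 response to predict later response; the plan gives no information on either. Subjects are not said to be told their area measurement, so dropout may follow perceived benefit instead. In the study described in 1.6.3, 84.3% of quantitative responders were also responders on masked review, so the two are related but not identical. Section 5.7 asks withdrawing subjects for last-visit assessments, 5.8 requires repeated contact attempts, and someone lost after Day 180 keeps that record. Every Day-90 non-responder still counts in the primary analysis.

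A reader might also infer that the omission favours Simulines. That rests on a hypothetical 10-point Day-90 deficit, the change is small against sampling error, its direction is not general, and no non-inferiority test is planned at these days.

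It can fairly be added that the endpoint is consistently defined at Days 180 and 365 (synopsis, 5.3.2, 6.4.3.2.1), that keeping Day 90 out avoids a second Day-90 estimate, and that a new model leaves the raw labelling proportions unchanged.

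These arguments limit the size and certainty of the point. They do not remove it. Subjects lost to follow-up give no exit measurement, the plan does not say how an early-exit measurement would count as Day 180 or 365, and Day-90 data relevant to the missing visits go unused.

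**Conclusion.** The gap is real and minor. The model omits an identically measured earlier response and gives no weight to subjects seen only at Day 90. The Day 180/365 proportions may therefore be biased: upward if non-responders leave more often, downward if responders do, and not at all if dropout is unrelated to Day-90 response or that response has no bearing on later response. For 5% to 16% loss and two to three times higher dropout in non-responders, the illustrative size is about 1 to 3 points (0.5 to 3.2 in the table). That range rests on assumed persistence and dropout, not on figures in the plan. The effect on the arm contrast is small and of no fixed direction. The endpoints are supportive, and the primary Day-90 conclusion is unaffected.

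**What to change.** In 6.4.3.2.1, include Day-90 response as a repeated outcome with Days 180 and 365, for all ITT subjects with at least one post-treatment area measurement. Fit by maximum likelihood (for example, a logistic model with a subject random effect) with study group, day and a group-by-day interaction. The interaction is needed because main effects alone would force one common arm effect and pull the later contrasts toward Day 90. Take the Day-180 and Day-365 contrasts and the marginal (population-averaged) proportions from this model. Report those proportions beside the observed ones wherever Day 180/365 response is shown, including labelling.

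The cost is SAP wording, since the Day-90 data are already collected for the primary analysis. There are three downsides. A second, model-based Day-90 estimate will exist, so the SAP should state that the primary Z-test remains the Day-90 result. The model-based proportions may be slightly less favourable than the observed ones. Validity still assumes a correctly specified model and dropout that depends only on observed responses; dropout driven by unseen later outcomes is not corrected.
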